2.2.4.2. OLE Baseline

The OLE Baseline for the 6MWT will use the PRONTO Baseline for 6MWT. Otherwise, OLE Baseline is defined as the last assessment prior to first infusion in the OLE.

2.3. Study Endpoints

2.3.1. Safety Endpoints

Safety evaluations performed during the study include:

- Vital signs
- 12-lead ECGs
- Routine laboratory assessments
- AEs
- Immunogenicity

2.3.2. Efficacy Endpoints

The following are the efficacy endpoints.

2.3.2.1. NT-proBNP (Cardiac) Endpoints

The following endpoints will be evaluated in the NEOD001 Safety Population and OLE Safety Population (see Section 5).

For these subjects, cardiac response, as assessed by N-terminal pro-brain natriuretic peptide (NT-proBNP), categories are defined as (modified from Table 2 in [Comenzo, 2012; Appendix 2](#)):

Response	Stable Disease	Progression
Decrease in NT-proBNP from baseline of >30% and >300 ng/L	Assessment was neither Response nor Progression	Increase in NT-proBNP from baseline of >30% and from baseline >300 ng/L

Best response is defined as the most favorable category (response, stable, or progression) across all visits. Subjects will be classified as responders or non-responders. Non-response is defined as either stable or progression.

- Cardiac best response from PRONTO and OLE baselines (see Section 2.2.4), as assessed by NT-proBNP response criteria. Best response will be over the course of the study.
- Cardiac response from PRONTO and OLE baselines (see Section 2.2.4), as assessed by NT-proBNP response criteria, at each visit
- Change and percent change from PRONTO and OLE baselines (see Section 2.2.4) to each visit in NT-proBNP

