Efficacy data from the completed Study NEOD001-001 were reported by Gertz et al. (2016) and are summarized herein. Cardiac response was assessed by the clinically relevant cardiac biomarker, NT-proBNP, using Comenzo et al, 2012 criteria (Appendix 3). Thirty-six subjects were considered cardiac evaluable (i.e., baseline NT-proBNP ≥ 650 pg/mL). Among cardiac-evaluable subjects, 53% (n=19) met the criteria for cardiac best response and 47% (n=17) met cardiac best response category of stable disease. Renal response was defined according to Palladini et al (2014) criteria (Appendix 3). Thirty-six subjects were considered renal evaluable (i.e., baseline proteinuria ≥ 0.5 g/24 hours). Among renal-evaluable subjects, 64% (n=23) met the criteria for renal best response and 36% (n=13) met renal best response category of stable disease. Peripheral neuropathy response was defined according to Coelho et al (2012) criteria (Appendix 3). Eleven subjects in the Peripheral Neuropathy Expansion Cohort were considered peripheral neuropathy evaluable. Among peripheral neuropathy-evaluable subjects, 82% (n=9) met the criteria for neuropathy response (i.e., < 2 -point increase in Neuropathy Impairment Score–Lower Limbs [NIS-LL] score [88-point scale] from baseline) and 18% (n=2) were progressors. Two of the responders had complete resolution of peripheral neuropathy.

Eligible subjects from Study NEOD001-001 are being enrolled in Study NEOD001-OLE001, an open-label extension study to evaluate the long-term safety and tolerability of NEOD001 in subjects with AL amyloidosis. Subjects receive 24 mg/kg NEOD001 once every 28 days using the infusion duration established for the individual subject in Study NEOD001-001 or over 60 (± 10) minutes.

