8. EFFICACY ANALYSES

All recorded efficacy endpoint data will be presented in by-subject data listings for the OLE Safety Population.

Analyses will be produced in both NEOD001 Safety Population and OLE Safety Population, unless otherwise specified. Data, visit window, and treatment group to be used for each population as below:

1. NEOD001 Safety Population:
 - Data: Pooled data from parent and OLE study
 - Visit window: PRONTO visit window for data in parent study, OLE therapy visit window for OLE data with exclusion of OLE Baseline.
 - Treatment: Placebo and NEOD001 subjects received in NEOD001-201 study and Overall
2. OLE Safety Population:
 - Using data from OLE study only
 - Visit window: OLE therapy visit window
 - Treatment: NEOD001

Analyses in Renal Evaluable Population or Peripheral Neuropathy Evaluable Population will be presented in the same manner described above for NEOD001 Safety Population and OLE Safety Population.

Baseline in all efficacy analyses refers to PRONTO Baseline and OLE Baseline, unless otherwise specified.

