APPENDIX 2. ORGAN RESPONSE AND PROGRESSION CRITERIA

Organ	Response	Progression
Heart/Cardiac ^{a,b}	NT-proBNP response (>30% and >300 ng/L decrease in subjects with baseline NT-proBNP \geq 650 ng/L) OR NYHA class response (\geq 2 class decrease in subjects with baseline NYHA class III or IV) ^b	NT-proBNP progression (>30% and >300 ng/L increase) ^c
Renal ^d	\geq 30% decrease in proteinuria or drop of proteinuria below 0.5 g/24 hours in the absence of renal progression	\geq 25% decrease in eGFR
Peripheral Nerve ^e	NIS-LL increase from baseline of <2 points	NIS-LL increase from baseline of \geq 2 points

Abbreviations: ALP = alkaline phosphatase; eGFR = estimated glomerular filtration rate; NIS-LL = Neuropathy Impairment Score–Lower Limbs; NT-proBNP = N-terminal pro brain natriuretic peptide; NYHA = New York Heart Association.

a Modified from Table 2 in [Comenzo 2012](#).

b NYHA class not considered for primary efficacy endpoint analyses.

c Subjects with progressively worsening renal function cannot be scored for NT-proBNP progression.

d [Palladini 2014](#).

e [Coelho 2012](#).

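### SAP 2.3.2.1 scores NT-proBNP response without the baseline ≥650 ng/L condition that both appendices attach to it, and Section 10 does not record a change

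*SAP*

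**What the plan says.** The scoring table in SAP 2.3.2.1 gives response as "Decrease in NT-proBNP from baseline of >30% and >300 ng/L". No baseline level is required. The sentence above the table reads "The following endpoints will be evaluated in the NEOD001 Safety Population and OLE Safety Population", and the endpoints listed below it are reported from both baselines. SAP 8 confirms this: "Baseline in all efficacy analyses refers to PRONTO Baseline and OLE Baseline, unless otherwise specified". For NT-proBNP, the second baseline comes from SAP 2.2.4.2: "Otherwise, OLE Baseline is defined as the last assessment prior to first infusion in the OLE". It is therefore measured after the parent study.

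SAP 2.3.2.1 describes its categories as modified from a published table and cites Appendix 2. The Response column of Appendix 2 reads ">30% and >300 ng/L decrease in subjects with baseline NT-proBNP" ≥650 ng/L. Protocol Appendix 3 has the same condition, and Protocol 3.2.2 defines NT-proBNP response by reference to that appendix. In both appendices the floor is in the Response column only. The Progression column has no baseline floor.

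SAP 5 defines renal and peripheral neuropathy evaluable populations but no cardiac one. Protocol 8.1 bases all analyses on the Safety Population and names only renal, neuropathy and hepatic subsets. SAP 8.6.1 and 8.6.2 add no floor. SAP Section 10, which lists changes to the protocol's analyses, does not mention it.

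**The concern.** Two programmers working from the same SAP could produce different cardiac response rates. One following the 2.3.2.1 table would count a qualifying fall from any baseline. One following Appendix 2 would not count it below 650 ng/L. The reader of the study report could not tell which rule was used.

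The conflict matters most for OLE Baseline. OLE eligibility (Protocol 4.1 and 4.2) sets no NT-proBNP minimum, and some subjects may have improved during the parent study. At stake is whether the reported response and best-response rates are the endpoint that the protocol defines.

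**Working it through.** **1. The documents' own cardiac rate.** Protocol 1.2.2 states "Thirty-six subjects were considered cardiac evaluable", meaning baseline ≥650 pg/mL (the same as ng/L), with 19 responders and 17 stable. 19/36 = 52.8% and 17/36 = 47.2%, which reproduce the stated 53% and 47%. That rate used the floor as its denominator rule.

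**2. What the rule demands at each baseline.** The fall must exceed max(0.30 × baseline, 300 ng/L).

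| Baseline (ng/L) | Fall must exceed | As % of baseline | Response under SAP 2.3.2.1 | Response under Appendix 2 |
|---|---|---|---|---|
| 300 | 300 | 100% | impossible | not allowed |
| 400 | 300 | 75.0% | possible | not allowed |
| 500 | 300 | 60.0% | possible | not allowed |
| 600 | 300 | 50.0% | possible | not allowed |
| 649 | 300 | 46.2% | possible | not allowed |
| 650 | 300 | 46.2% | possible | possible |

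Example: 600 to 295 is a fall of 305 ng/L, and 305/600 = 50.8%. The two rules disagree only for baselines above 300 and below 650.

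**3. Why OLE Baseline is the sensitive case.** A parent-study responder has fallen by more than 300 ng/L from PRONTO Baseline. If PRONTO Baseline is 650 to 950 and the response still holds at OLE entry, OLE Baseline is below 950 − 300 = 650. Such a subject must start the OLE under the floor.

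**4. Separating the two effects.** Let f be the share of subjects below 650, p the response rate among those at or above it, and q the share of those below who meet the 2.3.2.1 rule.

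- A, floor applied and denominator ≥650: p
- B, floor applied and all subjects in the denominator: (1 − f)p
- C, SAP 2.3.2.1 as written: (1 − f)p + fq

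Omitting the floor, with the denominator unchanged, gives C − B = fq, which is never negative. The all-subject denominator gives B − A = −fp, which is never positive. The net difference is C − A = f(q − p), and its sign depends on whether q is below or above p.

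**5. Illustration.** Assumptions: N = 100 (the approximate size in Protocol 3.3) and p near the Phase 1/2 rate. Neither f nor q is in the documents. Counts are rounded to whole subjects (for q = 25%: 2 of 10, 5 of 20, 8 of 30).

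| f | A | B | C, q = 0 | C, q = 25% | C, q = 50% |
|---|---|---|---|---|---|
| 0 | 53/100 = 53% | 53% | 53% | 53% | 53% |
| 10% | 48/90 = 53.3% | 48% | 48% | 50% | 53% |
| 20% | 42/80 = 52.5% | 42% | 42% | 47% | 52% |
| 30% | 37/70 = 52.9% | 37% | 37% | 45% | 52% |

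At f = 20% and q = 25%, omitting the floor adds 0.20 × 0.25 = 5 points, the denominator removes 0.20 × 0.525 = 10.5 points, and the net is −5.5 points. Over all possible q at f = 20%, the net runs from −10.5 points (q = 0) to 0.20 × (1 − 0.525) = +9.5 points (q = 1).

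**The case against.** The sponsor can fairly answer as follows.

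- **The floor is not gone.** Appendix 2 still carries it, and 2.3.2.1 cites that appendix. This stands: a reader might infer that the SAP abolished the floor, but what it contains is an unreconciled conflict. Describing the categories as modified does not settle it, because nothing says that the floor is the part modified. Where Appendix 2 sets an element aside (NYHA class, for the primary efficacy analyses), it says so in a footnote.
- **The denominator is the protocol's.** Protocol 8.1 planned no cardiac subset. Under the appendix rule with that denominator, a subject at ≤300 ng/L is still counted as a non-responder. This stands. A reader might blame the missing floor for diluting the rate, but step 4 shows that the omission alone can only add responders.
- **Subjects below 650 are still scorable.** A reader might infer that they are not evaluable at all. The appendices do not say that: a rise from 600 to 1000 ng/L is progression under both appendices and under 2.3.2.1. This stands, and it limits the fix.
- **Re-baselining is declared.** OLE Baseline adds an analysis beside PRONTO Baseline and replaces nothing, so it is not itself an error.
- **Little rides on the rate.** There is no control group and no power basis, the SAP was cut back after the programme ended, and no comparison with the Phase 1/2 rate is planned. This keeps the point modest but does not tell a programmer which rule to use.

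**Conclusion.** The point holds as an internal contradiction. The response rule in SAP 2.3.2.1 is not the rule in SAP Appendix 2 and Protocol Appendix 3, and Section 10 does not record the difference. Followed as written, 2.3.2.1 can count responders whom the appendices exclude (baseline above 300 and below 650 ng/L). It also keeps in the denominator subjects who cannot respond (≤300 ng/L), and Protocol 8.1 shares responsibility for that second effect.

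The size cannot be derived from the documents. They do not give the share of subjects below 650 at either baseline, nor the parent study's NT-proBNP entry threshold. If no subject is below 650, or if those below respond at the same rate as the rest, the net effect is zero. The percentages in the illustration rest on assumed f and q and are not a forecast. No claim that the reported rate will be too low, or too high, is supported. The correction is worth making before the tables are run.

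**What to change.** 1. In SAP 2.3.2.1, add the Appendix 2 condition to the Response category, applied to whichever baseline is in use (PRONTO or OLE).
2. In SAP 8.6.1 and 8.6.2, report response versus non-response, with the exact CI, among subjects whose relevant baseline is ≥650 ng/L, and give the count below 650. The all-subject rate may stay as a supplementary row.
3. Keep progression scoring and change from baseline on all subjects. In the three-category table a subject below 650 can be stable or progression only. State that such a subject is not missing response status, because SAP 8.2.2 would otherwise class that subject as progressed for best response.
4. If the floor was dropped on purpose, say so in Section 10 and correct Appendix 2.
5. While editing, settle one related gap: the Appendix 2 footnote "Subjects with progressively worsening renal function cannot be scored for NT-proBNP progression" is also absent from 2.3.2.1.

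The cost is a few lines of SAP text and one programming flag per baseline, with no new data. The response denominator becomes somewhat smaller: in the illustration the exact 95% CI is 41.0% to 63.8% for 42/80, against 32.2% to 52.3% for 42/100. For the OLE-baseline rate the denominator is also selected on NT-proBNP level at OLE entry, so it leaves out some subjects who improved in the parent study. The count below 650 and the supplementary row make that visible.

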Appendix 3 Organ Response and Progression Criteria

Organ	Response	Progression
Heart ^a	NT-proBNP response (>30% and >300 ng/L decrease in subjects with baseline NT-proBNP \geq 650 ng/L) OR NYHA class response (\geq 2 class decrease in subjects with baseline NYHA class III or IV)	NT-proBNP progression (>30% and >300 ng/L increase) ^b
Renal ^c	\geq 30% decrease in proteinuria or drop of proteinuria below 0.5 g/24 hours in the absence of renal progression	\geq 25% decrease in eGFR
Liver ^a	50% decrease in abnormal ALP value OR \geq 2 cm reduction in liver size radiographically	\geq 50% increase in ALP above the lowest value
Peripheral Nerve ^d	NIS-LL increase from baseline of <2 points	NIS-LL increase from baseline of \geq 2 points

ALP = alkaline phosphatase; eGFR = estimated glomerular filtration rate; NIS-LL = Neuropathy Impairment Score–Lower Limbs; NT-proBNP = N-terminal pro-brain natriuretic peptide; NYHA = New York Heart Association.

- a Modified from Table 2 in [Comenzo et al, 2012](#). In addition to the progression criteria listed above, the investigators will use their best clinical judgment in circumstances that do not meet the specifically referenced criteria above in assessing the progression. A repeated assessment at an interval that is determined by the investigator is required to confirm the progression.
- b Subjects with progressively worsening renal function cannot be scored for NT-proBNP progression.
- c [Palladini et al, 2014](#).
- d [Coelho et al, 2012](#).

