2.2. Study Design

2.2.1. Overall Study Design

This is a global, multicenter, Phase 2b, open-label extension study of subjects with AL amyloidosis who completed Study NEOD001-201. Subjects in this study may receive concomitant chemotherapy.

Subject screening will occur during the 28 days prior to the first administration of study drug (i.e., Month 1-Day 1 Visit), which may overlap with the last visit in Study NEOD001-201. If all eligibility requirements are met, the subject will be enrolled and Screening assessments will be completed. Screening assessments are listed in [Table 1](#).

Study visits will occur every 28 days based on scheduling from Month 1-Day 1. A ± 5 -day window is allowed for visits starting after Month 1. Subjects may receive up to 36 infusions of study drug. Subjects who discontinue study drug before the End of Study (EOS) Visit should have an Early Treatment Discontinuation (ETD) Visit 30 (± 5) days after their final administration of study drug.

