8.6. NT-proBNP (Cardiac) Endpoint Analyses

8.6.1. Best Response from Baseline

Best response will be derived from Baseline. All visits after the first infusion of study drug will be included. The number and percentage, with associated two-sided exact (Clopper-Pearson) 95% CIs, of subjects in each category of best response (response, nonresponse) will be presented. Refer to [Section 8](#) for details about course of the study and relative first infusion of study drug for each set of analyses.

Cardiac response as 3 categories (response, stable, and progression) will be presented in the same manner described above.

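### Best cardiac response takes the most favorable of up to 36 monthly NT-proBNP values with no confirmation, so the rate rises with visit count even without a drug effect, and that table hides worsening

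*SAP*

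**What the plan says.** For cardiac best response, SAP 2.3.2.1 states: "Best response is defined as the most favorable category (response, stable, or progression) across all visits". SAP 8.6.1 sets the scope: "All visits after the first infusion of study drug will be included". It reports counts and percentages with exact 95% CIs, in two categories and again in three.

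The thresholds in SAP 2.3.2.1 apply to a single assessment. Response is "Decrease in NT-proBNP from baseline of >30% and >300 ng/L" and progression is "Increase in NT-proBNP from baseline of >30% and from baseline >300 ng/L". SAP Appendix 2 limits the first to a baseline of at least 650 ng/L ("NT-proBNP response (>30% and >300 ng/L decrease in subjects with baseline NT-proBNP" and so on), a condition that 2.3.2.1 does not repeat. Protocol Appendix 3, note a, covers heart and liver: "A repeated assessment at an interval that is determined by the investigator is required to confirm the progression". Neither document asks for a response to be confirmed, and SAP Appendix 2 does not carry over the repeat for progression.

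On frequency, SAP 2.2.1 states "Study visits will occur every 28 days based on scheduling from Month 1-Day 1" and "Subjects may receive up to 36 infusions of study drug". Table 1 has NT-proBNP at every monthly visit and at EOS/ETD.

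SAP 8.6.2 repeats the 8.6.1 analysis at each visit, and 8.6.3 adds an MMRM of change from baseline. Under 8.2.2, missing best-response status counts as non-response, or as progression in the three-category table, while by-visit response uses observed cases. SAP section 10 removes progression-free survival and time to organ progression.

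**The concern.** One low value against one baseline makes a subject a responder permanently, whatever follows. The reported proportion is thus driven by the lowest of many noisy values, and it depends on how long each subject was followed. A subject with one stable or low early value who then deteriorates never appears as a progressor in this table.

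Best response is the first efficacy result listed in the SAP, and the OLE-only analysis has a single arm. Nothing in that analysis shows what rate to expect without a drug effect, and the CI reflects sampling error only. A reader could take a sizeable percentage as benefit when some or all of it is visit-to-visit variation.

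**Working it through.** **The plan's own figures.** The OLE states no null rate, sample size or power. The nearest figure is the Phase 1/2 result in Protocol 1.2.2: 19/36 = 52.8% response and 17/36 = 47.2% stable. Since 19 + 17 = 36, no subject had progression as best category. This fits the pattern described here but does not prove it.

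**Number of values.**
- OLE baseline: Months 2-36 give 35 predose draws, plus EOS = 36.
- PRONTO baseline, pooled data: 11 (Months 2-12) + 1 (end-of-study visit) + 36 = about 48.
- By OLE Month 12 a subject has 11 scheduled post-baseline values, so the 12-visit figures below slightly overstate that window.

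**Two consequences that need no assumption about noise.** The maximum over visits cannot fall when a visit is added, so the no-effect responder rate can only rise. The worst category can be the best one only if every observed value falls in it, or if status is missing.

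**One visit, no true change.** Assume log-normal within-subject variation with log-SD s, on baseline and on each visit. Above 300/0.30 = 1000 ng/L the 30% condition is the binding one. With independent values, the chance of response at one visit is Φ(ln 0.7 / (s√2)). At s = 0.20 this is Φ(-0.357/0.283) = Φ(-1.26) = 10.4%.

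**Many visits.** Treating visits as fully independent would give 1 - (1 - 0.104)^12 = 73% at 12 visits and 98% at 36. Both are too high, because all visits share one baseline. Simulation with a shared baseline (100,000 subjects per setting) gives these no-effect rates. The ranges cover visit-to-visit correlations between 0 and 0.8:

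| Assumed log-SD | One fixed late visit | Best of 12 | Best of 36 | Two consecutive visits, within 36 |
|---|---|---|---|---|
| 0.10 | 0.6% | 1-5% | 5-10% | 1-3% |
| 0.15 | 5% | 11-26% | 27-40% | 11-18% |
| 0.20 | 10% | 25-44% | 46-61% | 25-35% |
| 0.25 | 16% | 36-57% | 60-73% | 37-48% |

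For best-of-12 and best-of-36, the lower end is correlation 0.8 and the upper end is independence. At log-SD 0.20, 6 visits give 12-33% and 48 visits give 52-65%. With independent values and log-SD 0.15-0.25, confirmation within 12 visits gives 6-24%.

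**True worsening.** Let NT-proBNP double steadily over 12 visits, starting from 2000 ng/L, with independent noise and log-SD 0.15-0.25:
- best category progression: 5-8%
- best category response: 4-24%
- progression rule met at some visit: 98% or more
- planned by-visit table: 59-65% progression at visit 6 and 89-98% at visit 12

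**An any-visit progression count has the same fault.** With no true change, log-SD 0.25 and correlation 0.8, 49% meet the progression rule at least once in 12 visits.

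**The case against.** Four stronger readings are tempting, and the documents do not support them.

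- *True progression is almost never shown.* This holds for the best-response table only. SAP 8.6.2 gives the three categories at each visit and 8.6.3 models the change. In the doubling scenario the by-visit table shows the worsening plainly. Individual values are also listed. Two limits remain: by-visit response drops subjects who have left, and no planned table counts how many subjects progressed by NT-proBNP.
- *The inflation is large.* That depends on a within-subject SD that the documents do not give. At log-SD 0.10 it is modest, and correlation between monthly values lowers it.
- *Subjects had 36 visits, or very unequal follow-up.* Thirty-six is a maximum. SAP section 10 says the program was discontinued, so actual counts may be well below it, and the documents do not report them.
- *The exact CIs present the rate as a drug effect.* SAP 8.6.1 has no test, null rate or success criterion, so the intervals are descriptive.

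Two features work against overstating benefit. Missing best-response status counts as non-response, and the pooled analysis is shown by parent-study treatment. However, parent-study placebo subjects who enter the OLE receive NEOD001, so they are not a clean reference over the pooled period.

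Replacing the endpoint with a confirmed rate would also redefine a protocol endpoint, and the confirmed rate would still be inflated. That objection stands, so the remedy should be an addition.

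**Conclusion.** The concern holds in a limited form. Best cardiac response is an unconfirmed best-of-all-visits statistic whose no-effect rate rises with follow-up, and its three-category table is one-sided toward benefit. Both statements follow from the rule itself.

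The size is conditional. Under no true change and 12 visits, it is about 11-57% for an assumed log-SD of 0.15-0.25 and correlation of 0.8 to 0, and about 1-5% at log-SD 0.10. The rate cannot be read as a drug effect without a reference rate. Worsening is not lost from the analysis as a whole. What is missing, after the removals in SAP section 10, is a per-subject summary of NT-proBNP progression.

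**What to change.** Keep the protocol-defined best response, and in SAP 8.6.1 add beside it:

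(a) response criteria met at two consecutive scheduled visits, by OLE Month 6 and by OLE Month 12, with all dosed subjects as denominator;

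(b) the number of subjects meeting the progression rule at two consecutive visits in the same windows, and the category at the last visit;

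(c) the number of NT-proBNP assessments per subject.

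State in the text that the unconfirmed rate is not to be read as a drug effect without a reference rate, and that confirmation reduces the inflation but does not remove it. Item (c) also lets the reader see how many subjects had too few visits to be confirmed, since an all-dosed denominator counts them as non-responders.

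The cost is SAP wording, programming and a few more tables on data already collected, with no added visits. The drawback for the sponsor is a lower, less favorable response figure next to the planned one.

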Due to the limited number of infusion-site related reactions reported to date, premedication of subjects prior to the start of NEOD001 infusion is not required in the NEOD001-OLE001, NEOD001-201, and NEOD001-OLE251 protocols. As of 30 September 2016, 221 subjects had been dosed in the 4 completed or ongoing studies. In Study NEOD001-CL002 (VITAL), 129 subjects received a total of 534 infusions of blinded study drug (24 mg/kg NEOD001 plus standard of care or placebo plus standard of care). In Study NEOD001-201 (PRONTO), 23 subjects received a total of 51 infusions of blinded study drug (24 mg/kg NEOD001 or placebo). In Study NEOD001-001, 69 subjects received 994 infusions of NEOD001 (up to doses of 24 mg/kg) and 31 of these subjects had gone on to receive 59 infusions of 24 mg/kg NEOD001 in the open-label extension study (NEOD001-OLE001). In the completed Study NEOD001-001, 6 subjects experienced 9 infusion-site reactions were reported (6 subjects) and most (n=7; 78%) were classified as Grade 1. As noted above, 1 subject in the ongoing Study NEOD001-201 experienced an event of vasovagal syncope (characterized by bradycardia, hypotension, and syncope). Another aspect of safety monitoring in studies of NEOD001 has been a required postinfusion observation time ranging from 60 to 120 minutes. Studies NEOD001-201 and NEOD001-OLE251 allow for flexibility in monitoring time if no reactions are seen after the first 2 infusions, as described in Section 5.3.

Based on the data available to date, NEOD001 has been well tolerated as single-agent therapy in subjects with AL amyloidosis and no clinically significant safety signals have been identified.

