2.3.2.4. Renal Endpoints

The following endpoints will be evaluated in the Renal Evaluable Population (see Section 5).

For these subjects, renal response categories (modified from [Palladini, 2014](#) ; [Appendix 2](#)) are defined as:

Response	Stable	Progression
≥ 30% decrease from baseline or < 0.5g/24 hours post-baseline result of proteinuria (measured by 24-hour urine total protein excretion) in the absence of renal progression	Assessment was neither Response nor Progression	≥ 25% decrease in eGFR from baseline Note: if assessment qualifies as both Response and Progression, then assessments will be counted as progression

Best response is defined as the most favorable category (response, stable, or progression) across all visits. Subjects will be classified as responders or non-responders. Non-response is defined as either stable or progression.

- Renal best response from PRONTO and OLE baselines (see Section 2.2.4). Best response will be evaluated over the course of the study
- Renal response from PRONTO and OLE baselines (see Section 2.2.4) at each visit
- Change and percent change from PRONTO and OLE baselines (see Section 2.2.4) to each visit in creatinine, proteinuria, and estimated glomerular filtration rate (eGFR)

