10. CHANGES TO PROTOCOL PLANNED ANALYSES

Due to the discontinuation of the NEOD001 program, the following changes were made to any protocol planned analyses:

1. All safety analyses were removed except AE overview, TEAEs and SAEs.
2. The below efficacy analyses were removed:
 - Change from baseline in troponin T
 - Change from baseline in the Short Form-36 Health Survey version 2 (SF-36v2) Mental Component Score (MCS) and the 8 subscales
 - Progression-free survival
 - For renal-evaluable subjects:
 - Time to eGFR:
 - Time to any worsening in CKD Stage
 - Time to 40% reduction in eGFR
 - Time to doubling of creatinine
 - For peripheral neuropathy-evaluable subjects:
 - Peripheral neuropathy best response
 - Peripheral neuropathy response
 - For subjects with painful peripheral neuropathy in Study NEOD001-201 (i.e., baseline Visual Analog Scale – Pain Intensity [VASPI] score >0) change from baseline in the VASPI score
 - For hepatic-evaluable subjects:
 - Hepatic response
 - Hepatic best response from baseline
 - Frequency and duration of hospitalizations over the course of the study
 - Change from baseline in the Kansas City Cardiomyopathy Questionnaire (KCCQ) subscores and overall summary score
 - Time to progression for each organ (cardiac/NT-proBNP, renal, peripheral neuropathy, hepatic) separately and to any organ progression
 - Eastern Cooperative Oncology Group (ECOG) Performance Status and New York Heart Association (NYHA) Class at each visit including any changes from baseline
 - Change from baseline in serum free light chains (sFLCs), serum and 24-hour urine protein electrophoresis (PEP), and serum and urine immunofixation electrophoresis (IFE)
 - Severity of disease-related symptoms including any changes from baseline

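### In the OLE-only analysis, best cardiac and renal response is a crude percentage over unequal follow-up, and the SAP does not adapt it to the programme's discontinuation

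*SAP*

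**What the plan says.** SAP 2.3.2.1 states: "Best response is defined as the most favorable category (response, stable, or progression) across all visits". It adds "Non-response is defined as either stable or progression" and sets the period with "Best response will be over the course of the study". SAP 2.3.2.4 uses the same construction for the kidney: "Best response will be evaluated over the course of the study".

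SAP 8.6.1 says "All visits after the first infusion of study drug will be included" and reports the number and percentage in each category with exact 95% intervals. SAP 8.9.1 applies this to renal best response. Neither section sets a minimum follow-up, a fixed window or censoring.

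On planned length, SAP 2.2.1 says "Subjects may receive up to 36 infusions of study drug". Protocol 3.6 allows participation of up to 38 months, or until the study is terminated.

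SAP Section 10 opens with "Due to the discontinuation of the NEOD001 program, the following changes were made to any protocol planned analyses". Its list removes many endpoints, including time to organ progression, but does not touch best response.

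The only missing-data rule for best response is in SAP 8.2.2. Missing status becomes non-response in the two-category table and progression in the three-category table, whatever the reason.

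**The concern.** Best response accumulates with time: the longer a subject is observed, the more chances there are to meet the criterion once. A simple percentage can be interpreted if everyone is observed for a known, similar period. After a sponsor stop, each subject's observation period depends on when that subject entered relative to the stop.

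SAP 8.2.2 does not reach the main case. A subject with two stable assessments before the stop is not missing; that subject is a full non-responder.

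The renal endpoint is more exposed. In the schedule of assessments (Table 1 of both documents), OLE 24-hour urine is collected every 6 months and at EOS/ETD. SAP Section 5 makes renal evaluability depend on parent-study proteinuria only. A subject stopped before the first six-monthly collection may have only the ETD sample, or none. With no OLE urine result, and so no response status, 8.2.2 records non-response or progression even if the sponsor's stop was the cause.

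At stake is how the OLE response rate is read in a study meant to describe long-term efficacy. The exact interval reflects sampling error only, not the mix of follow-up times.

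**Working it through.** The plan has no sample size, expected OLE response rate or follow-up distribution, so there is no design figure to reproduce. Two background figures agree: 19/36 = 52.8% (Protocol 1.2.2 gives 53%), and 1 + 36 + 1 = 38 months (Protocol 3.6).

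**Inputs from the documents.** Eventual cardiac best response p = 19/36, from the cardiac-evaluable subjects of the Phase 1/2 study (Protocol 1.2.2). N of about 100 (Protocol 3.3).

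**Assumptions, not in the documents.** Time to response among eventual responders is exponential with median m of 3, 6 or 12 months. Follow-up at the stop is spread evenly over whole months from a to b.

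**Formulas.** True cumulative response at t months: F(t) = p × (1 − 2^(−t/m)). Expected crude best response: the mean of F(f) over f = a, …, b.

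**Example, m = 3.** F(12) = 0.528 × (1 − 1/16) = 49.5%. For m = 6, 0.528 × (1 − 1/4) = 39.6%. For m = 12, 0.528 × 1/2 = 26.4%.

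| m (months) | True, 12 mo | True, 36 mo | Crude, 1–6 | Crude, 1–12 | Crude, 1–18 | Crude, 6–18 |
|---|---|---|---|---|---|---|
| 3 | 49.5% | 52.8% | 27.4% | 36.9% | 41.7% | 48.1% |
| 6 | 39.6% | 52.0% | 16.9% | 25.8% | 31.8% | 38.3% |
| 12 | 26.4% | 46.2% | 9.5% | 15.8% | 20.9% | 25.8% |

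**Against 36 months.** The crude rate is always lower. With follow-up starting at 1 month, the shortfall runs from 52.8 − 41.7 = 11.1 points to 46.2 − 9.5 = 36.7 points.

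**Against 12 months.** With follow-up of 1–12 months, the crude rate is 49.5 − 36.9 = 12.6, 39.6 − 25.8 = 13.8 and 26.4 − 15.8 = 10.6 points low. With 6–18 months the gaps are 1.4, 1.3 and 0.6 points. The sign can reverse: if the stop came 12 months after the last entry, with entry spread over 6 to 18 months and m = 3, the crude rate is 51–52% against 49.5%.

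**Interval.** At N = 100 and follow-up of 1–12 months, the Clopper-Pearson limits for 37, 26 and 16 responders are 27.6–47.2%, 17.7–35.7% and 9.4–24.7%. Each lies wholly below its own 12-month value (49.5%, 39.6%, 26.4%).

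**Comparator.** In 4,000 simulated studies of 100 subjects, one minus Kaplan-Meier at 12 months, censoring at last assessment, came within 0.5 points of the true value in every setting tried (follow-up 1–12, 1–18 and 6–18 months).

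**The case against.** The strongest reply is that the plan already contains fixed-time results. Cardiac and renal response at each visit (SAP 8.6.2, 8.9.2) use observed cases, so subjects cut off leave both numerator and denominator. NT-proBNP change is modelled by visit (8.6.3). The NEOD001 Safety Population analysis pools parent and OLE data (Section 8). Exposure duration and infusions are summarised (9.1), so truncation will be visible. Early stoppers should have an ETD visit. The study has no primary endpoint or hypothesis, and the protocol always allowed follow-up to end at termination. All of this stands. It confines the problem mainly to the OLE-only best-response table, but it does not give that table a time horizon or link exposure to it.

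A reader might infer that nobody could reach Month 36. The protocol notes that in the parent study, by 30 September 2016, "23 subjects received a total of 51 infusions of blinded study drug", against about 100 planned for the OLE, which suggests late entry. But no document gives OLE entry dates or the stop date. Trying plausible dates does not settle it: entry over at most 18 months and a stop at most 12 months later caps follow-up at 30 months, while Month 36 falls at 35 × 28 = 980 days, or 32.2 months. Zero is then built in.

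A reader might also infer that late entrants all become non-responders, or that the rate is biased downward against any horizon. Early responders keep their response, and the 12-month comparison can go either way.

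**Conclusion.** The point holds for the OLE Safety Population. Best cardiac and renal response is a proportion over whatever follow-up each subject had, and the SAP, although revised because of the discontinuation, neither adapts it nor states the follow-up reached. Against the full planned follow-up the direction is certain: the rate is too low. Against 12 months neither the sign nor the size can be fixed from the documents. Under the assumptions above, the gap runs from about 11–14 points low (follow-up 1–12 months) to within about 1.5 points (6–18 months), and it is slightly positive if all subjects have at least 12 months and responses come early. These figures rest on assumed follow-up and response times, and on a response rate borrowed from another study.

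The renal consequence under 8.2.2 assumes that a subject without an OLE urine result has missing status; the SAP does not say whether eGFR alone could make that subject stable.

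The documents do not support saying that the SAP has no missing-data rule or no fixed-time response analysis. Because the analysis is descriptive, this is a worthwhile, inexpensive improvement rather than a fault that invalidates the plan.

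**What to change.** In SAP 8.6.1 and 8.9.1, for the OLE Safety Population:

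- Add the cumulative incidence of first response at OLE Month 6 and Month 12 with 95% CIs. Censor subjects stopped by programme termination at their last assessment, and treat death as a competing event.
- Label the crude percentage as over available follow-up, and show the median and range of follow-up beside it.

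In SAP 8.2.2, do not class subjects with no OLE assessment because of sponsor termination as progressed.

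The cost is SAP wording and standard output. Visit dates and response data exist, Kaplan-Meier with censoring is already planned for survival (8.11), and discontinuation reasons are already tabulated from the eCRF (7.1). The downsides are wider intervals, coarse timing for renal response (urine every 6 months plus ETD), and the need to check that the eCRF reason identifies sponsor termination, which the documents do not show.
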